1 INTRODUCTION

The purpose of this document is to give details for the statistical analysis of study D6580C00010 Part A supporting the clinical study report. The reader is referred to the CSP and the CRF for details of study conduct and data collection.

2 CHANGES TO PROTOCOL PLANNED ANALYSES

A standard deviation of 20 points was assumed for KCCQ-TSS for the sample size calculations. No other changes to planned analyses.

3 DATA ANALYSIS CONSIDERATIONS

3.1 Timing of Analyses

At least two, but possibly several, interim analyses will be performed by an internal study-independent Unblinded Review Committee (URC), with the purpose of informing further development of the clinical programme, including but not limited to dose selection to start Part B. The first interim analysis will be performed when at least 150 randomised subjects have had the possibility to reach the 16 weeks visit. One of the interim analyses will be performed when all subjects in Part A have completed the last protocol-specified visit/assessment. If Part B were not to start or progress, then the last interim analysis of Part A would be regarded as the final analysis and this will be used to write the CSR.

In addition, a Data Review Committee (DRC) will perform periodic analyses with focus on skin reactions and rashes, and general safety. These analyses are not in scope for this document and are described in a separate DRC charter.

3.2 Analysis Populations

See Sections 4.2, 4.6 and 4.2.16.1 for definitions of estimand populations.

3.3 General Considerations

3.3.1 General Study Level Definitions

3.3.1.1 Baseline

For the Full analysis set (FAS, see Section 4.1.2.1), baseline is defined as the last non-missing value prior to or on the day of randomisation, including unscheduled assessments that occur prior to the randomisation visit, for each subject and endpoint. If administration of the first dose of investigational product should happen to occur prior to randomisation, baseline will be defined as the last non-missing value on or before the day of the first dose.

For the Safety analysis set (SAS, see Section 4.1.2.1), baseline is defined as the last non-missing value prior to or on the day of first administration of IP, including unscheduled assessments that occur prior to the first dose visit, for each subject and endpoint.

If two assessments taken at the same day qualify as baseline, the following will apply:

- If the variable is qualitative, then the worst value from a clinical perspective will be used as the baseline value.
- For KCCQ, the first assessment (value) will be used as baseline.
- For handling of cases when more than one value could qualify as baseline for any other reason, see Section 3.3.3.

3.3.1.2 Handling of incomplete dates

The following imputed dates will only be used for analysis purposes and will remain as reported (partially or completely missing) in subject listings.

Incomplete IP stop dates

Partially missing IP stop dates will be imputed as follows:

- If the day value of last dose is missing, the first day of the month will be used; unless this occurs in the same month and year as the date of a known administration of IP, then this date will be used.

Incomplete adverse event dates

Partially or completely missing adverse event (AE) onset dates will be imputed as follows:

- If only the day value of the adverse event onset date is missing, the first day of the month will be used; unless this occurs in the same month and year as the latest of randomisation and date of first dose of IP, then the latest of randomisation and the date of first dose of IP will be used.
- If the day and month values of the adverse event onset date are missing, January 1 will be used; unless this occurs in the same year as the latest of randomisation and the date of first dose of IP, then the latest of randomisation and the date of first dose of IP will be used.
- If the adverse event onset date is completely missing, the latest of randomisation and the date of first dose of IP will be used.

Incomplete death dates

Partially or completely missing death dates will be imputed as follows:

- If only the day value of the death date is missing, the first day of the month will be used; unless this occurs in the same month and year as last visit date, the last visit date will be used.
- If the day and month values of the death date are missing, January 1 will be used; unless this occurs in the same year as last visit date, then last visit date will be used.
- If the death date is completely missing, last visit date will be used.

Incomplete efficacy event dates

Partially or completely missing event onset dates will be imputed as follows:

- If only the day value of the event onset date is missing, the first day of the month will be used; unless this occurs in the same month and year as randomisation, then the date of randomisation will be used.
- If the day and month values of the event onset date are missing, January 1 will be used; unless this occurs in the same year as randomisation, then the date of randomisation will be used.
- If the event onset date is completely missing, the date of randomisation will be used.

Incomplete concomitant medication dates

For medications that started prior to study start, start day will not be imputed. Partially or completely missing concomitant medication (CM) start dates will be imputed as follows:

- If only the day value of the CM start date is missing, the first day of the month will be used; unless this occurs in the same month and year as the date of randomisation, then the date randomisation will be used
- If the day and month values of the CM start date are missing, January 1 will be used; unless this occurs in the same year as the date of randomisation, then the date randomisation will be used.
- If the CM start date is completely missing, the date of randomisation will be used.

If medication is marked as ‘Treatment continues’ the stop date will not be imputed. Partially or completely missing CM stop dates (where applicable) will be imputed as follows:

- If only the day value of the CM stop date is missing, the last day of the month will be used; unless this occurs in the same month and year as the last visit, then the date of the last visit will be used.
- If the day and month values of the CM stop date are missing, December 31 will be used; unless this occurs in the same year as the last visit, then the date of the last visit will be used.
- If the CM stop date is completely missing, the date of the last visit will be used.

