3.3.1.5 Study periods

Study periods for Full Analysis Set (FAS)

Screening period

The screening period starts at the date of signed informed consent and ends at the day before randomisation. For subjects enrolled but not randomised, the enrolment period ends at last visit.

Planned treatment period

The follow-up time for the Planned treatment period will be calculated from randomisation and to the earliest of day of visit 11 (if subject attended visit 11, otherwise day 343 will be used), date of withdrawal of consent or date of death. If withdrawal of consent or death did not occur, it

will be calculated from randomisation and to the earliest of day of visit 11 (if subject attended visit 11, otherwise day 343 will be used) or the last study visit.

Study periods for Safety Analysis Set (SAS)

Pre-treatment period

The pre-treatment period starts at the date of signed informed consent and ends before the date and timepoint of first dose of IP.

On-treatment period

The follow-up time for the On-treatment period will be calculated from the date of the first dose of IP and to the earliest of 14 days after last dose, date of withdrawal of consent or date of death. If withdrawal of consent or death did not occur, it will be calculated from the date of the first dose of IP and to the earliest of 14 days after last dose of study drug or the last study visit..

On-study period

The follow-up time for the On-study period will be calculated from the date of the first dose of IP and to the earliest date of withdrawal of consent or date of death. If withdrawal of consent or death did not occur, it will be calculated from the date of the first dose of IP and to the last study visit.

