4.6 Safety Analyses

The domain safety covers exposure, adverse events, clinical laboratory, vital signs, and electrocardiogram (ECG).

Tables, figures, and listings are provided for SAS unless otherwise stated. All tabulations of safety data (AEs, laboratory parameters, vital signs, and ECG) will be based on both the On-treatment period and On-study period respectively unless otherwise stated.

The analyses will be presented for AZD4831 2.5mg, AZD4831 5mg, AZD4831 Total (pooled treatment groups AZD4831 2.5mg and 5mg) and placebo, unless otherwise stated.

Safety estimand definition

The aim with the analyses of safety data is to assess the general safety objective; this will be done for a hypothetical scenario where study treatment is not prematurely discontinued. Two different handling of intercurrent event strategies are considered complementary to assess this hypothetical scenario for all safety endpoints:

- On-treatment; unbiased under the assumption that censoring following premature treatment discontinuation is non-informative. Note that this approach could also be described as handling premature treatment discontinuation with a hypothetical strategy.
- On-study; unbiased under the assumption that the risk for an event is independent of continued treatment. Note that this approach could also be described as handling premature treatment discontinuation with a treatment policy strategy.

Hence, the general safety objective will be assessed through two complementary estimands with respect to handling of the intercurrent event of premature discontinuation of study treatment, defined by the following attributes:

- **Population:** Subjects with an established diagnosis of HF with LVEF > 40%, as defined by the inclusion and exclusion criteria, who have received at least one dose of IP. Implemented using the safety analysis set.
- **Treatment:** Actual treatment group (i.e., not necessarily the treatment a subject was randomised to), AZD4831 2.5mg/5mg or placebo.
- **Intercurrent events:**
 - Premature study treatment discontinuation: All analyses will be provided using two complementary strategies:
 - Hypothetical strategy: Premature study treatment discontinuation cannot occur, implemented by censoring data after premature study treatment discontinuation + 14 days, using the On-treatment analysis period (Section 3.3.1.5).

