4.6.2 Adverse Events

4.6.2.1 Definitions and Derivations

Adverse event will be assigned to the analysis period based on the onset date, as defined in Section 3.3.1.5.

Adverse events will be classified by SOC and PT and coded using Medical Dictionary for Regulatory Activities (MedDRA).

Risk for an event will be estimated using KM% estimates. Comparisons of risk for an event between the treatment groups will be estimated by HRs with 95% CIs based on a Cox regression model with a factor for treatment group, and difference in KM%. A subjects first event that occurs during the On-treatment or On-study period, respectively, will be included in the analysis. All subjects who are event free for the given AE (or AE category) will be censored according to the definitions in Sections 3.3.1.5 and 3.3.1.8.

Any AE

Defined as an AE reported with an onset date within the defined period.

Any SAE

Defined as an AE reported as serious, irrespective of outcome.

SAEs with outcome death

Defined as an AE with reported outcome as 'Fatal', there may be more than one AE with outcome death for a subject. The onset date of the AE determines the analysis period, irrespective of date of death.

AEs leading to discontinuation of IP

Defined as an AE with action taken IP reported as drug permanently discontinued. The onset date of the AE determines the analysis period, irrespective of date of discontinuation of IP.

AEs possibly related to IP

Defined as an AE that is reported as "reasonable possibility AE caused by IP". If this evaluation is missing, it will be counted as an AE possibly related to IP.

AEs by maximum intensity

AEs will be classified by the reported maximum intensity, "Mild", "Moderate" and "Severe". If this maximum intensity evaluation is missing, it will be counted as "Severe".

Adverse events of special interest

The following two groups of adverse events are Adverse events of special interest (AEoSI):

- Infections: will be identified by the SOC "Infections and infestations".
 - The pathogen specific High level group term (HLGT) "Fungal infectious disorders".
- Skin reactions, including maculopapular rash:
 - Skin reactions/rashes considered maculopapular (described as macules/papules under the morphology/appearance question).
 - Skin reactions/rashes not considered maculopapular (not described as macules/papules under the morphology/appearance question).

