4.6.2.2 Presentation

For all AE tables, unless otherwise stated, the number and percentage of subjects experiencing an event along with Kaplan-Meier percentages at 16 and 48 weeks will be presented for all treatment groups. In addition, KM% differences and HR together with 95% confidence intervals will be presented for the comparisons of each active treatment group to placebo. Percentages will be calculated with number of subjects in SAS as denominator, and subjects will only be counted once per category, regardless of the number of AEs satisfying each condition.

Tables where AEs are presented by SOC and PT will be sorted by international order for SOC and alphabetical order for PT.

In addition, KM% estimates of the cumulative distribution function of subjects with AEoSIs will be plotted comparing all treatment groups. Overall summary of AEs

The following categories will be presented in the overall summary:

- any AE,
- any SAE,
- any SAE with outcome death,
- any AE leading to discontinuation of IP, and
- any AE possibly related to IP (as assessed by investigator).

Any AE leading to discontinuation of IP category will only be analysed for the On-treatment period.

By SOC and PT

Separate AE tables by SOC and PT will be presented for the following categories:

- any AE,
- AEs possibly related to IP,
- AEs leading to discontinuation of IP,
- AEs by cumulative maximum intensity (any, moderate or severe, severe),
- any SAE,
- SAE with outcome death, and

- AEs of special interest.

Most common AEs

A table of the number and percentage, and KM% at 16 and 48 weeks of the most common adverse events by PT (frequency of > 5%). This table will be sorted by decreasing frequency in AZD4831 5mg arm.

Most common non-serious AEs

A table of non-serious AEs occurring in more than 5% of subjects in any treatment group will be presented, by SOC and PT.

AEs of special interest

A mapping of the AEoSIs to Preferred terms will be presented.

For each of the SOC Infections and infestations and the HLGT Fungal infectious disorders, an overall summary, and any AE and SAE by PT will be presented. In the overall summaries, AEs by cumulative maximum intensity (any, moderate or severe, severe) will be presented in addition to categories described under Overall summary of AEs.

Skin reactions will be presented by a summary of the following categories of skin reactions:

- any skin reaction/rash

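### When the day of the last dose is missing, the SAP imputes it early, which can end on-treatment follow-up before treatment stopped and drop the adverse event that caused the stop from one summary

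*SAP*

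**What the plan says.** All the rules are in the Part A SAP.

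- **Imputation (3.3.1.2).** For the study drug: "If the day value of last dose is missing, the first day of the month will be used". The exception is "unless this occurs in the same month and year as the date of a known administration of IP", in which case the administration date is used.
- **Window (3.3.1.5).** On-treatment follow-up runs from first dose "to the earliest of 14 days after last dose", withdrawal of consent or death. Without withdrawal or death, it runs to the "earliest of 14 days after last dose of study drug or the last study visit".
- **Placing the event (4.6.2.1).** For adverse events that led to stopping the drug: "The onset date of the AE determines the analysis period, irrespective of date of discontinuation of IP".
- **Which period is reported (4.6.2.2).** Under the overall summary: "Any AE leading to discontinuation of IP category will only be analysed for the On-treatment period". The general rule in 4.6 is wider, though it allows for exceptions: "All tabulations of safety data (AEs, laboratory parameters, vital signs, and ECG) will be based on both the On-treatment period and On-study period respectively".
- **A different stop date (3.3.1.2).** For concomitant medication: "If only the day value of the CM stop date is missing, the last day of the month will be used", or the last visit date if that falls in the same month.

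The imputed stop date presumably also feeds duration of exposure (4.6.1.1) and the expected number of doses for compliance (4.1.12.1).

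**The concern.** Each rule is reasonable alone. Together they can exclude an event from the row designed to count it. The imputed last dose is the first of the month or a dose known to have been taken, so its error runs one way: it should never be later than the true last dose. If the true date is late in the month, the 14-day tail can expire while the participant is still taking the drug. An event that begins after that point and causes the stop is then outside the on-treatment period. No rule keeps it in on the ground that it led to discontinuation, and that overall-summary row has no on-study counterpart.

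The rule also departs from the safety estimand in SAP 4.6, whose hypothetical strategy censors 14 days after premature discontinuation. Under the imputation, censoring can come before discontinuation, so the participant enters the Kaplan-Meier and Cox analyses as event-free shortly before the event.

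**Working it through.** The plan gives no figure on this point, so there is none to reproduce. What follows is date arithmetic.

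**Inputs.** Imputation rule and exception: SAP 3.3.1.2. Window: SAP 3.3.1.5. Site dosing on visit days: Protocol 6.4. Part A site visits on Days 1, 29, 85, 113, 169, 253 and 336: Protocol Table 1. Assumptions: the day is missing, the true last-dose date is equally likely to be any day in the range considered, and onset is 0, 3, 7 or 14 days before the last dose.

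**Worked example, no known June dose.** True last dose 28 June; event onset 26 June. Imputed last dose 1 June; cutoff 1 + 14 = 15 June. The true cutoff would be 12 July. The event falls outside the imputed window.

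**No known dose in the month.** Let the month have L days and the true last dose be on day D. The cutoff is day 15.

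- Mean shortening = mean of (D − 1) = (L − 1)/2: 14.5 days for L = 30 and 15.0 for L = 31.
- An event with onset *lag* days earlier is lost if D − lag > 15, which holds for L − 15 − lag of the L days. For L = 30 and lag 0: 15/30 = 50%.

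**Known dose on day k.** The cutoff is k + 14. In a 31-day month loss is still possible when k + 14 < 31, that is k ≤ 16. The exception reduces the problem without removing it.

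**Part A visit spacing.** I took all 365 randomisation dates in a year and all last-dose study days from 2 to 335, treating site-visit doses as the known administrations. In 72% of these cases there is no known dose in the month of the last dose. Mean shortening over all cases is 12.0 days.

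Share of discontinuation events lost, among participants with a missing stop day:

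| Onset before last dose | No known dose, 30-day month | No known dose, 31-day month | Part A spacing, site doses known |
|---|---|---|---|
| 0 days | 15/30 (50%) | 16/31 (52%) | 37% |
| 3 days | 12/30 (40%) | 13/31 (42%) | 28% |
| 7 days | 8/30 (27%) | 9/31 (29%) | 17% |
| 14 days | 1/30 (3%) | 2/31 (6%) | 2% |

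**Early rash.** Protocol 4.3 reports rash in healthy volunteers about 7 to 10 days after first dose, which is study days 8 to 11. With the drug stopped 0 to 3 days after onset, there are 365 × 4 × 4 = 5840 scenarios. None is lost, because the first dose is a known administration and the tail is 14 days.

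**Compliance.** This assumes the imputed date defines the end of expected dosing. In the example the denominator loses 28 − 1 = 27 days while the pill count is unchanged. With D days from first dose to imputed last dose, a fully compliant participant scores (D + 27)/D, which exceeds 120% when D < 27/0.20 = 135 days.

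**Last day of the month instead.** The share lost falls to 0% at every lag. Without a cap, the last dose is placed 14.7 days too late on average.

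**The case against.** The case for leaving the rule alone has several strong parts.

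- **Rarity.** Protocol 6.4 requires stop dates in the eCRF, and Protocol 7.1 calls for an early discontinuation visit. The documents give no count of partial dates. This stands: every percentage above is conditional on a missing day.
- **The event is reported elsewhere.** It stays in the on-study tables for other adverse event categories, in listings, in narratives and in the key subject information, which for these events covers the full study (SAP 4.6.2.2). The on-treatment-only sentence sits under the overall summary. Whether it also governs the table by system organ class and preferred term is not explicit, and the skin summary carries no such restriction of its own. This stands: a reader might infer that the event disappears from safety reporting, and it does not.
- **Rash.** A reader might infer that rash discontinuations are hit hardest. The documents do not support that. Nothing shows that partial dates cluster there, these cases get an extra clinic visit and a dedicated eCRF page (Protocol 8.2.5), and no early-rash scenario was lost.
- **Direction of bias.** The rule applies equally to all arms and removes follow-up time as well as events. No direction is shown for the Kaplan-Meier difference or hazard ratio, so calling the treatment comparison anti-conservative would go too far.
- **Different purposes.** A late stop date for concomitant medication avoids overlooking a co-medication; an early one for study drug avoids crediting undocumented dosing as exposure. The contrast therefore does not prove an error. It does show that the SAP already accepts late imputation bounded by a visit date.

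None of this repairs the chain of rules for the overall-summary row.

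**Conclusion.** The point holds as a minor one. As written, the SAP can end on-treatment follow-up before the true last dose and leave the event that ended treatment out of the overall-summary row for such events. Exposure is shortened too, and so is the compliance denominator if it uses the same date.

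Among participants with a missing stop day, the size is about 12.0 days of mean shortening and 37%, 28%, 17% or 2% loss at lags of 0, 3, 7 or 14 days. A mean of 14.5 days and a loss of 50% are the worst case for a 30-day month with no known dose in it and should not be quoted as the general size. The lower figures rest on a uniform last-dose date and on site-visit doses being the only known administrations. SAP 3.3.1.2 does not limit the term that way, and the dosing card in Protocol 6.4 could supply further dates, which would lower the figures.

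**What to change.** Replace the rule in SAP 3.3.1.2 with: a missing last-dose day is imputed as the earliest of the last day of that month, the date of the early discontinuation visit, the last study visit date and the date of death, and no earlier than any known administration in that month.

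Do not add a floor at the onset of a discontinuation event. That would lengthen follow-up only for participants who had the event being counted, making the risk window depend on the outcome.

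The cost is one SAP sentence and a line of code. The downside is that exposure may be overstated by some days in the affected cases. The 14.7-day average applies without caps; the visit and death dates can only reduce it. I have not enumerated the capped version.

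### An incomplete death date is checked only against the last visit, so a participant can be dated dead before a fully dated event, which then leaves the AE tables and its CV component analysis

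*SAP*

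**What the plan says.** SAP 3.3.1.2 has three rules for incomplete death dates.

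- Day missing: "If only the day value of the death date is missing, the first day of the month will be used", with the exception "unless this occurs in the same month and year as last visit date, the last visit date will be used".
- Day and month missing: "If the day and month values of the death date are missing, January 1 will be used", or the last visit date if that falls in the same year.
- Nothing known: "If the death date is completely missing, last visit date will be used".

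No rule looks at an AE onset, a CV event, a hospital admission, a dose or a sample. The IP stop-date rule in the same section does yield to a later known fact: "unless this occurs in the same month and year as the date of a known administration of IP, then this date will be used".

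The imputed date then sets the end of follow-up. SAP 3.3.1.5 runs the On-study period "from the date of the first dose of IP and to the earliest date of withdrawal of consent or date of death". The On-treatment period and the Planned treatment period also close at death if nothing earlier closes them. SAP 3.3.1.8 includes an event only when its onset lies in the period analysed, and censors event-free participants on the period's last day. For SAEs with a fatal outcome, SAP 4.6.2.1 adds: "The onset date of the AE determines the analysis period, irrespective of date of death". SAP 4.2.16.2 applies the Planned treatment period to the CV endpoint.

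**The concern.** Each rule is ordinary alone, but together they can produce an impossible order of dates. A participant whose fatal event is dated to the day, and whose death is dated only to the month, can be recorded as dead before that event began. The event then lies beyond the end of follow-up. In the fatal-SAE analysis the participant is censored as event-free, although the mortality analysis counts the death. For the same person, the safety tables would contradict the mortality result and the narrative.

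The data structure allows this. Protocol 8.3.2 collects AE start, hospitalisation date and date of death as separate items. Protocol 7.3 allows vital status to be taken from public sources, which is a plausible route to a partial death date.

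**Working it through.** The plan states no figure for this point, so there is none to reproduce. The check applies the written rules to example dates.

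**Example (invented dates).** Randomisation and first dose 1 Sep 2022; fatal AE onset 10 Mar 2023, fully dated; true death 18 Mar 2023. Study day = date − 1 Sep 2022 + 1, so onset is day 191. The On-study period ends at the imputed death. The On-treatment period ends then or earlier.

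| Known about death | Last visit | Imputed death | Period ends | AE (day 191) | Death moved early by |
|---|---|---|---|---|---|
| Month and year | 20 Feb 2023 | 1 Mar 2023 | day 182 | excluded | 17 days |
| Month and year | 5 Mar 2023 | 5 Mar 2023 | day 186 | excluded | 13 days |
| Year only | 20 Dec 2022 | 1 Jan 2023 | day 123 | excluded | 76 days |
| Nothing | 20 Feb 2023 | 20 Feb 2023 | day 173 | excluded | 26 days |

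**CV endpoint.** Suppose the 10 March event is an HF hospitalisation. It falls after the Planned treatment period has closed, so it is lost from its component analysis. SAP 4.2.16.4 keeps component events that follow a non-fatal event of another type; it does not keep events dated after death. The composite still has an event, the death at the imputed date. Its timing is wrong by 191 − 182 = 9, 191 − 186 = 5, 191 − 123 = 68 and 191 − 173 = 18 days in the four rows.

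**How often a dated event is lost, given that the situation arises.** Assume that only the day is missing, the last visit was in an earlier month, death is uniform over a 31-day month, and the event began L days before death. The event is lost when death day − L > 1, which is (30 − L)/31.

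- L = 0: 30/31 = 97%
- L = 3: 27/31 = 87%
- L = 7: 23/31 = 74%
- L = 14: 16/31 = 52%
- L = 28: 2/31 = 6%

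**How many participants.** Protocol 2.2 gives 50-75 deaths per 1000 patient-years as background for HFpEF trial populations. It is not a study assumption. With 660 participants for one year:

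- deaths: 660 × 0.050 = 33 to 660 × 0.075 = 49.5
- partial death dates at an assumed 2-5%: 33 × 0.02 = 0.7 to 49.5 × 0.05 = 2.5
- times the loss fraction for L = 14 down to L = 3: 0.66 × 16/31 = 0.3 to 2.475 × 27/31 = 2.2

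The last line is an upper bound. It treats every partially dated death as having a fully dated event before it, for which the documents give no rate.

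**With a floor at the last known-alive date.** In all four rows the imputed death becomes 10 Mar 2023, day 191, and the event is inside the period.

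**The case against.** Several objections carry weight.

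- **Two conditions must coincide.** A participant with a dated admission for a fatal event is the one whose death date is least likely to be missing. Partial dates are likelier for people traced through public sources, who are less likely to have a dated SAE. This stands, and it keeps the count low.
- **The imputation rules often agree.** If the AE also lacks its day, it moves to the first of the month, or to the later of randomisation and first dose if that is in the same month. A same-month AE then normally stays in. This stands, so the problem is confined to fully dated events.
- **Fatal SAEs may be protected.** SAP 4.6.2.1 assigns them by onset regardless of when death occurred, which could be read as a rule against dropping them. That wording chooses which date assigns the event; it does not extend a period that SAP 3.3.1.5 closes at death. At best the text is ambiguous.
- **Nothing formal depends on it.** Safety analyses are descriptive without p-values (Protocol 9.4.3), the CV endpoint is exploratory, and the tested hypotheses in SAP 3.3.4 do not use these periods. This stands.

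A reader might infer that the participant disappears from the CV analysis, or that the event disappears from the report. The documents support neither. CV death and all-cause mortality are components of the composite (SAP 4.2.16.1), so the death is counted, only too early. SAP 4.6.2.2 lists every AE and requires narratives for all deaths and SAEs, and SAP 3.3.1.2 keeps reported dates in listings.

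**Conclusion.** The point holds as a minor defect in a stated rule. With an incomplete death date and a later, fully dated event, the SAP removes that event from the On-treatment and On-study AE tables. It also removes a non-fatal HF hospitalisation, urgent HF visit or MI from its component analysis, and misdates the composite.

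The likely size is 0 to about 2 participants in Part A, and possibly none. That range rests on the assumed 2-5% rate of partial dates and on a background mortality range, so it should not be quoted as an expected count or as a share of an arm's fatal events. The case for acting is that the rule can yield an impossible sequence and conflicting tables for one participant, and that it is very cheap to correct.

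**What to change.** Replace the death-date rule in SAP 3.3.1.2 with the following. Impute death as the latest of:

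- (a) the first day of the known month or year;
- (b) the last visit;
- (c) the last date the participant is known to have been alive, taken only from fully recorded, non-imputed dates (AE or CV event onset, admission, dose, sample or contact).

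Cap the result at the end of the known month or year. If the death date is completely missing, use the later of (b) and (c).

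Limiting (c) to recorded dates stops one imputed date from driving another. The cost is a short SAP edit and a few lines in the death-date derivation. It needs no new data collection, and it brings the death rule into line with the IP stop-date rule in the same section.
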